11. SAFETY MONITORING

11.1. Adverse Events and Serious Adverse Events

11.1.1. Definition of Adverse Events

An AE is any untoward medical occurrence associated with the use of an intervention in humans, whether or not considered intervention-related (21 CFR 312.32 (a)). When an AE is deemed to be related to the study device, it is termed an adverse device event.

11.1.2. Definition of Serious Adverse Events

An AE or suspected adverse reaction is considered serious if, in the view of either the investigator or Sponsor, it results in any of the following outcomes: death, a life-threatening AE, inpatient hospitalization or prolongation of existing hospitalization, a persistent or significant incapacity or substantial disruption of the ability to conduct normal life functions, or a congenital anomaly/birth defect. Important medical events that may not result in death, be life-threatening, or require hospitalization may be considered serious when, based upon appropriate medical judgment, they may jeopardize the participant and may require medical or surgical intervention to prevent one of the outcomes listed in this definition. When a serious AE is deemed to be related to the study device, it is termed a serious adverse device event (SADE).

11.2. Unanticipated Adverse Device Event

An unanticipated adverse device event (UADE) is defined in 21 CFR Part 812.3(s) as “any serious adverse effect on health or safety or any life-threatening problem or death caused by, or associated with, a device, if that effect, problem, or death was not previously identified in nature, severity, or degree of incidence in the investigational plan or application (including a supplementary plan or application), or any other unanticipated serious problem associated with a device that relates to the rights, safety, or welfare of subjects”.

Other important medical events which may not result in any of the outcomes above, but which may require intervention to prevent one of the outcomes above, may in the opinion of the investigator, be considered a UADE.

11.3. Classification of an Adverse Event or Adverse Device Event

11.3.1. Severity of Event

All AEs will be assessed by the study clinician using a protocol defined grading system as follows:

- Mild – Events require minimal or no treatment and do not interfere with the participant's daily activities.

Document ID:	SRC_SLE_Sparkle_P SG_2020_10908	Document title:		Classification:	Confidential
Modified:	26 July 2021	Clinical Investigation Protocol ICH E6 Aligned			
Version:	5	User Tool ID:	16.2.6UserTool0004		
Status:	Final	User Tool Version Date	5June2019	Page:	33

- Moderate – Events result in a low level of inconvenience or concern with the therapeutic measures. Moderate events may cause some interference with functioning.
- Severe – Events interrupt a participant's usual daily activity and may require systemic drug therapy or other treatment. Severe events are usually potentially life-threatening or incapacitating. Of note, the term "severe" does not necessarily equate to "serious".

11.3.2. Relationship to the Study or Device

All AEs will have their relationship to study procedures and the study device assessed by the clinician who examines and evaluates the participant based on temporal relationship and his/her clinical judgment. The degree of certainty about causality will be graded using the categories below.

- Definitely Related – There is clear evidence to suggest a causal relationship, and other possible contributing factors can be ruled out. The clinical event, including an abnormal laboratory test result, occurs in a plausible time relationship to study intervention administration and cannot be explained by concurrent disease or other drugs or chemicals. The response to withdrawal of the study intervention (dechallenge) should be clinically plausible. The event must be pharmacologically or phenomenologically definitive, with use of a satisfactory rechallenge procedure if necessary.
- Probably Related – There is evidence to suggest a causal relationship, and the influence of other factors is unlikely. The clinical event, including an abnormal laboratory test result, occurs within a reasonable time after administration of the study intervention, is unlikely to be attributed to concurrent disease or other drugs or chemicals, and follows a clinically reasonable response on withdrawal (dechallenge). Rechallenge information is not required to fulfill this definition.
- Potentially Related – There is some evidence to suggest a causal relationship (e.g., the event occurred within a reasonable time after administration of the trial medication). However, other factors may have contributed to the event (e.g., the participant's clinical condition, other concomitant events). Although an AE may rate only as "possibly related" soon after discovery, it can be flagged as requiring more information and later be upgraded to "probably related" or "definitely related", as appropriate.
- Unlikely to be related – A clinical event, including an abnormal laboratory test result, whose temporal relationship to study intervention administration makes a causal relationship improbable (e.g., the event did not occur within a reasonable time after administration of the study intervention) and in which other drugs or chemicals or underlying disease provides plausible explanations (e.g., the participant's clinical condition, other concomitant treatments).
- Not Related – The AE is completely independent of study intervention administration, and/or evidence exists that the event is definitely related to another etiology. There must be an alternative, definitive etiology documented by the clinician).

Document ID:	SRC_SLE_Sparkle_P SG_2020_10908	Document title:		Classification:	Confidential
Modified:	26 July 2021	Clinical Investigation Protocol ICH E6 Aligned			
Version:	5	User Tool ID:	16.2.6UserTool0004		
Status:	Final	User Tool Version Date	5June2019	Page:	34

11.3.3. Expectedness

The Principal Investigator will be responsible for determining whether an AE is expected or unexpected. An AE will be considered unexpected if the nature, severity, or frequency of the event is not consistent with the risk information previously described for the study intervention.

11.4. Adverse Event Assessment and Follow-Up

Within 1-7 days of completing Visit 2, a phone call will allow for the assessment of any possible AEs that may have become apparent in the intervening period. Events will be followed for outcome information until resolution or stabilization

All AEs including local and systemic reactions not meeting the criteria for a serious adverse event (SAE) will be captured on the appropriate (e)CRF. Information to be collected includes event description, time of onset, clinician's assessment of severity, relationship to study product (assessed only by those with the training and authority to make a diagnosis), and time of resolution/stabilization of the event. All AEs occurring while on study must be documented appropriately regardless of relationship. All AEs will be followed to adequate resolution.

Any medical condition that is present at the time that the participant is screened will be considered as baseline and not reported as an AE. However, if the study participant's condition deteriorates at any time during the study, it will be recorded as an AE.

Changes in the severity of an AE will be documented to allow an assessment of the duration of the event at each level of severity to be performed. AEs characterized as intermittent require documentation of onset and duration of each episode.

11.5. Serious Adverse Event or Serious Adverse Device Event Reporting

The study investigator shall complete a SAE or UADE Form and submit to the Sponsor and to the reviewing IRB as soon as possible, but in no event later than 24 hours (for a SAE) or 10 working days (for a UADE) after the investigator first learns of the effect. The Sponsor is responsible for conducting an evaluation of the SAE/UADE and shall report the results of such evaluation to the Food and Drug Administration (FDA) and to all reviewing IRBs and participating investigators within 24 hours (for a SAE) or 10 working days (for a UADE) after the Sponsor first receives notice of the effect. Thereafter, the Sponsor shall submit such additional reports concerning the effect as FDA requests.

11.6. Device Deficiency

All device deficiencies, use or user errors, and equipment failures will be documented. Use or user errors will be captured as part of the source documentation. Device deficiencies and equipment failures will be kept on a separate log. The serial numbers and type of deficiency/failure will be captured. Unanticipated

Document ID:	SRC_SLE_Sparkle_P SG_2020_10908	Document title:		Classification:	Confidential
Modified:	26 July 2021	Clinical Investigation Protocol ICH E6 Aligned			
Version:	5	User Tool ID:	16.2.6UserTool0004		
Status:	Final	User Tool Version Date	5June2019	Page:	35

device deficiencies that lead or may lead to an SAE will be reported to the Sponsor within 24 hours of learning of the event.

11.7. Unanticipated Problems

11.7.1. Definition of Unanticipated Problems

An unanticipated problem (UP) is any incident, experience, or outcome that for which the nature, severity, or frequency is unexpected for the subject population or research activities as described in the current IRB approved protocol, supporting documents, and the consent form.

11.7.2. Unanticipated Problem Reporting

The Principal Investigator will submit to the Sponsor and to the reviewing IRB a report of any UADE occurring during an investigation as soon as possible, but in no event later than 10 working days after the investigator first learns of the effect (21 CFR 812.150(a)(1)). Under 812.46(b), the Sponsor shall report the results of such evaluation to the FDA and to all reviewing IRB's and participating investigators within 10 working days after the Sponsor first receives notice of the effect. Thereafter the Sponsor shall submit such additional reports concerning the effect as FDA requests (21 CFR 812.150(b)(1)).

Document ID:	SRC_SLE_Sparkle_P SG_2020_10908	Document title:		Classification:	Confidential
Modified:	26 July 2021	Clinical Investigation Protocol ICH E6 Aligned			
Version:	5	User Tool ID:	16.2.6UserTool0004		
Status:	Final	User Tool Version Date	5June2019	Page:	36

12. STATISTICAL CONSIDERATIONS

The statistical analysis plan has been incorporated into this protocol. It is not a stand-alone document.

12.1. Statistical Analyses

12.1.1. Sample Size Determination

The endpoint associated with Hypothesis 2 (ICC between PSG-CAI and DreamKit-CAI) exhibits a weaker effect size than the endpoint associated with Hypothesis 1 (ICC between PSG-AHI and DreamKit-AHI).

Pilot data from a sample of 178 records exhibited an ICC between the PSG-CAI and DreamKit-CAI 0.720 (95% CI 0.641 – 0.784). We will compare the lower-bound of the CI (0.641) to a threshold of 0.50, per Hypothesis 2. Assuming 90% power and an alpha of 0.05, $n=195$ participants will be required to test Hypothesis 2.

The same sample exhibited an ICC between the PSG-AHI and DreamKit-AHI of 0.908 (95% CI 0.879 – 0.931). We will compare the lower-bound of the CI (0.879) to a threshold of 0.75, per Hypothesis 1. Assuming 90% power and an alpha of 0.05, $n=56$ participants will be required to test Hypothesis 1. Thus, the sample size required for Hypothesis 2 ($n=195$) is more than adequate for Hypothesis 1, and we will adopt an overall sample size of $n=200$.

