12.1.2. General Considerations

The primary and secondary analyses will be performed after excluding studies that do not meet the AASM criteria for technical adequacy described in Section 8.1.6 (evaluable dataset). Continuous data will be presented by mean, standard deviation, median, minimum, and maximum observation. Data will be presented in the untransformed and transformed format (if applicable) for each continuous variable. Categorical data will be presented as frequencies and percentages. Significance tests will be conducted at a two-sided significance level of alpha of 0.05.

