12.1.5. Analysis of the Primary Endpoint

We will calculate the ICC for absolute agreement (two-way, mixed effect) between the AHI-PSG and DreamKit-AHI, along with a 95% CI. Hypothesis 1 will be supported if the lower-bound of the 95% CI is equal to or above 0.75.

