12.1.6. Analysis of the Secondary Endpoint

We will calculate the ICC for absolute agreement (two-way, mixed effect) between the AHI-CAI and DreamKit-CAI, along with a 95% CI. Hypothesis 2 will be supported if the lower-bound of the 95% CI is equal to or above 0.50.

For the primary and secondary endpoints, the AASM recommended definition of hypopnea will be used.

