12.1.7. Adjustment for Multiplicity

We have adopted a single primary endpoint, and will progress to the secondary endpoint only if the primary hypothesis is supported. There is therefore no requirement for an adjustment to control the false discovery rate.

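### Hypothesis 2 is sized at one-sided 5% but judged on a 95% CI: at the planning ICC of 0.641, n=200 gives about 84% power, not 90%

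*Combined protocol and SAP*

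**What the plan says.** Section 12.1.1 derives both sample sizes from a pilot of 178 records. For Hypothesis 2 the pilot ICC for the central apnea index (CAI) was 0.720 (95% CI 0.641 to 0.784), and the plan takes the lower limit as its planning value: "We will compare the lower-bound of the CI (0.641) to a threshold of 0.50, per Hypothesis 2". It then states: "Assuming 90% power and an alpha of 0.05, $n=195$ participants will be required to test Hypothesis 2". For Hypothesis 1 (apnea-hypopnea index, AHI) it sets the pilot lower limit of 0.879 against 0.75 and, at the same power and alpha, arrives at 56. Hypothesis 2 is the larger requirement, so it sets the study size, and 200 is adopted.

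The success rules come later. Section 12.1.5: "Hypothesis 1 will be supported if the lower-bound of the 95% CI is equal to or above 0.75". Section 12.1.6: "Hypothesis 2 will be supported if the lower-bound of the 95% CI is equal to or above 0.50". Section 4.2 and the synopsis state the hypotheses in the same terms. Section 12.1.2 adds: "Significance tests will be conducted at a two-sided significance level of alpha of 0.05". Under section 12.1.7 the study "will progress to the secondary endpoint only if the primary hypothesis is supported".

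Section 12 says that the statistical analysis plan is contained in the protocol, so no separate document supplies the missing sidedness.

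**The concern.** A power figure has to refer to the rule that decides success. Requiring the lower limit of a two-sided 95% CI to reach a threshold is a one-sided test at 0.025. If the sample size was worked out at one-sided 0.05, the trial is smaller than its own power statement requires. The 90% quoted for the hypothesis that sets the sample size is then too high, and a reader who applies the written decision rule cannot reproduce either 195 or 56.

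The CAI result bears on the intended-use claim in section 4.4 that the device can classify events as central, mixed or obstructive. An understated risk of missing it is therefore worth correcting, even for a secondary endpoint.

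**Working it through.** **Inputs (all from section 12.1.1 unless noted).** Hypothesis 2: planning ICC 0.641, threshold 0.50. Hypothesis 1: planning ICC 0.879, threshold 0.75. Power 90%, alpha 0.05 with sidedness not given. Two measurements per participant (PSG and DreamKit). Adopted n=200. Decision rule: lower limit of a 95% CI (sections 12.1.5 and 12.1.6).

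**Step 1: reproduce the plan's figures with Fisher z.** For two measurements, n = (z_alpha + z_beta)² / (atanh ICC1 − atanh ICC0)² + 1.5.

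- Hypothesis 2: atanh(0.641) − atanh(0.50) = 0.7599 − 0.5493 = 0.2106; squared, 0.04434.
- Hypothesis 1: atanh(0.879) − atanh(0.75) = 1.3714 − 0.9730 = 0.3984; squared, 0.15872.
- One-sided 0.05: (1.645 + 1.282)² = 8.564. This gives 8.564/0.04434 + 1.5 = 194.7, so **195**, and 8.564/0.15872 + 1.5 = 55.5, so **56**. Both stated figures are reproduced.
- One-sided 0.025: (1.960 + 1.282)² = 10.507. This gives 238.5, so **239**, and 67.7, so **68**. Neither stated figure is reproduced.

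**Step 2: check with the exact F test.** Power = P(F(n−1, n) > C0 × Fcrit), with C0 = (1 + 2t0)/(1 + 2t1) and t = ICC/(1 − ICC). For Hypothesis 2, t0 = 1 and t1 = 1.7855, so C0 = 3/4.571 = 0.6563. For Hypothesis 1, t0 = 3 and t1 = 7.2645, so C0 = 7/15.529 = 0.4508.

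| | One-sided 0.05 | One-sided 0.025 |
|---|---|---|
| H2: n for 90% power | 195 (power 90.06%) | 239 |
| H1: n for 90% power | 56 (power 90.32%) | 68 |
| H2: power at n=195 | 90.1% | 83.4% |
| H2: power at n=200 | 90.7% | 84.3% |
| H1: power at n=56 | 90.3% | 83.7% |
| H1: power at n=200 | >99.9% | >99.9% |

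With two-way degrees of freedom, F(n−1, n−1), the sizes are 196 and 56 at one-sided 0.05, and 239 and 69 at one-sided 0.025. Power for Hypothesis 2 at n=200 is then 84.2%. The choice of degrees of freedom does not matter to the conclusion.

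**Step 3: could 195 come from another planning value?** No. Planning on the pilot estimate of 0.720 needs 69 (one-sided 0.05) or 84 (one-sided 0.025).

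**Step 4: is the plan's 95% CI two-sided?** Yes. Fisher z with ICC 0.720 and 178 records has a standard error of 1/√176.5 = 0.0753. The two-sided 95% limits are tanh(0.9076 ± 1.96 × 0.0753) = 0.641 and 0.784, exactly as printed.

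**Step 5: power of the planned analysis itself.** The two-way absolute-agreement ICC and its confidence limits were simulated with normal data, no device bias, a true ICC of 0.641 and 20,000 runs (standard error about 0.003). With the 95% CI rule, power was 82.9% at n=195, 84.1% at n=200 and 90.2% at n=239. With a 90% CI at n=195 it was 89.9%, so the stated 90% appears only with a one-sided 0.05 bound.

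**Step 6: sensitivity to the true ICC at n=200, one-sided 0.025.** Power is 84.3% at 0.641, 89.9% at 0.652, 90.3% at 0.653 and 99.9% at 0.720.

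**Step 7: sensitivity to device bias.** The documents give no bias figure, so this is an assumption, in units of the total SD with the ICC held fixed. For Hypothesis 2 at 0.641 and n=200, simulated power is 84.4% at a bias of 0.1, 78.4% at 0.2 and 54.7% at 0.3. For Hypothesis 1 at 0.879 and n=200 it is 87.4% at 0.2.

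**The case against.** Section 12.1.1 never says that its alpha is two-sided. Read as one-sided, 195 and 56 are correctly computed, so this is an undeclared mismatch rather than a slip in calculation. That is fair as a description. It does not rescue the 90%, because the success rule is not one-sided 5% and nothing in the plan mentions a one-sided bound or a 90% CI.

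The sizing method is inferred. An approximate ICC formula (Walter, Eliasziw and Donner) gives 194.2 and 55.0, and exact F with two-way degrees of freedom gives 196. So one can say that the stated pair matches one-sided 0.05, not that a particular formula was used. The sentence on two-sided testing in section 12.1.2 concerns significance tests and is only supporting evidence. The mismatch rests on the CI rules in 12.1.5 and 12.1.6, which suffice.

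The strongest point is that little follows in practice. The planning value is already cautious, and at n=200 power reaches 90% at an ICC of about 0.653, only 0.012 above it. The endpoint is secondary and tested only after Hypothesis 1 succeeds, and the rule in force is the stricter one. All of this stands and limits the severity. But the plan itself attaches 90% power to 0.641, and that statement is not met.

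**Conclusion.** The concern holds. The stated 195 and 56 fit a one-sided 5% test, while success is judged at one-sided 2.5%. At the plan's own planning ICC of 0.641, n=200 gives about 84% power for Hypothesis 2, so the chance of missing it is about 16% rather than 10%. Reaching 90% would take 239 evaluable participants. The same mismatch in the Hypothesis 1 figure (56, against 68 or 69) is harmless because 200 are used.

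This should be fixed, but it does not threaten the trial: no false claim becomes more likely, and power is about 99.9% if the pilot estimate of 0.720 is right. The figures assume normally distributed data and no systematic difference between PSG and DreamKit. CAI is likely to be skewed, and a device bias of 0.2 SD or more could lower power noticeably.

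**What to change.** Keep n=200 and the 95% CI rule. In section 12.1.1:

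1. Name the sizing formula, and state that the test is the lower limit of a two-sided 95% CI, that is, one-sided 0.025.
2. Replace 195 and 56 with 239 and 68 as the sizes for 90% power at the planning values (69 instead of 68 if the formula named is the F test with two-way degrees of freedom).
3. Rewrite the closing sentence so that 239 is what 90% power would need at ICC 0.641 and 200 is what is adopted. Otherwise the section would call 239 required and then adopt fewer.
4. Report power at n=200: about 84% for Hypothesis 2 at ICC 0.641 (the pilot lower limit), 90% at about 0.653, about 99.9% at 0.720, and more than 99.9% for Hypothesis 1 at 0.879.
5. Add that these figures assume normal data and no systematic difference between devices, and that such a difference could lower power for an absolute-agreement ICC.

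The cost is wording in one section and one less favourable power figure. No extra participants are needed. Changing the success rule to a 90% CI to recover the 90% would relax the decision criterion and would need its own justification.

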12.1.2. General Considerations

The primary and secondary analyses will be performed after excluding studies that do not meet the AASM criteria for technical adequacy described in Section 8.1.6 (evaluable dataset). Continuous data will be presented by mean, standard deviation, median, minimum, and maximum observation. Data will be presented in the untransformed and transformed format (if applicable) for each continuous variable. Categorical data will be presented as frequencies and percentages. Significance tests will be conducted at a two-sided significance level of alpha of 0.05.

12.1.3. Participant Disposition

Participant disposition, including the total number of participants enrolled, completed, early terminations, and withdrawals, will be presented. A listing will be provided with the reasons for discontinuation.

12.1.4. Demographics and Baseline Characteristics

Participant demographics (age, sex, race/ethnicity) and descriptive characteristics will be summarized for all participants enrolled and for evaluable participants.

Document ID:	SRC_SLE_Sparkle_PSG_2020_10908	Document title:		Classification:	Confidential
Modified:	26 July 2021	Clinical Investigation Protocol ICH E6 Aligned			
Version:	5	User Tool ID:	16.2.6UserTool0004		
Status:	Final	User Tool Version Date	5June2019	Page:	37

12.1.5. Analysis of the Primary Endpoint

We will calculate the ICC for absolute agreement (two-way, mixed effect) between the AHI-PSG and DreamKit-AHI, along with a 95% CI. Hypothesis 1 will be supported if the lower-bound of the 95% CI is equal to or above 0.75.

12.1.6. Analysis of the Secondary Endpoint

We will calculate the ICC for absolute agreement (two-way, mixed effect) between the AHI-CAI and DreamKit-CAI, along with a 95% CI. Hypothesis 2 will be supported if the lower-bound of the 95% CI is equal to or above 0.50.

For the primary and secondary endpoints, the AASM recommended definition of hypopnea will be used.

12.1.7. Adjustment for Multiplicity

We have adopted a single primary endpoint, and will progress to the secondary endpoint only if the primary hypothesis is supported. There is therefore no requirement for an adjustment to control the false discovery rate.

